A total of 1ml (40 mg) will be injected intra-articularly after synovial fluid aspiration 'to dryness' either once (at study entry or 2 weeks after injury) or twice (at both study entry and 2 weeks after injury).

Rational for including pediatric population

The specific reason for enrolling the age group of children aged 14-17 is that these children have a musculoskeletal physiology like adults.

- Their major growth plates are closed.
- These patients may be treated surgically like adult patients with exactly the same surgical preparation, technique and rehabilitation as adults.
- Children, particularly girls, between the ages of 14 and 18 have the highest statistical risk in any population of tearing their Anterior Cruciate Ligament.²⁵
- Children in this age group are particularly vulnerable to the later development of osteoarthritis. Lohmander et al showed that young female soccer players in this age group developed symptomatic knee Osteoarthritis secondary to the ACL injury within 12 years of the injury.²⁴ One could therefore argue that particularly children between completed puberty and 18 years of age have to be the patients requiring most of our concern regarding development of OA.

By slowing the initial inflammatory process after injury and preventing the significant quadriceps muscle shutdown early, we aim to work towards this goal in this trial. We therefore conclude that given the limited risk of local side effects and the potential large benefit that this study would provide to the scientific community and its potential to significantly improve and alter patient care of young individuals suffering ACL injuries it is not reasonable to withhold pediatric patients aged 14-17 from this important trial.

RESEARCH OBJECTIVES OF THE CURRENT STUDY:

The research objectives of this study are:

1. Test the efficacy of Triamcinolone to alleviate knee pain (KOOS, IKDC) and improve patient-reported outcomes (PRO) following ACL rupture in a randomized, placebo controlled, double blinded, clinical trial. Triamcinolone will be administered intra-articularly within 1 week of ACL injury or at 2 weeks after ACL injury, or at both time points and compared with saline control injections. Patients will be evaluated at 5 post-injury time points (1-2 days, 12-14 days, 2 weeks post-op, 4 weeks post-op, 6 months

- post-op, and 24 months post-op) following ACL reconstruction.

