2. Determine if intra-articular Triamcinolone therapy improves levels of a panel of inflammatory (cytokine), meniscus and cartilage metabolism and oxidative stress biomarkers as measured in synovial fluid from patients at relatively short-term time points after ACL injury (1-7 days, 10-17 days after injury and at time of surgery). Biomarkers to be tested include IL-1 α , IL-1 β , Collagen type I (NtxI) and collagen type II (CTXII) breakdown products, cartilage oligomeric protein (COMP) and glycosaminoglycan (GAG) and Xanthine Oxidase. Additionally, the change in IL-1 α and IL-1 β levels in the Triamcinolone treated and placebo individuals will be evaluated specifically for association with pain and function outcomes.

RESEARCH OBJECTIVES OF EXTENDED FOLLOW-UP SUB-STUDY:

1. Determine if joint health as evaluated by MRI at 24 months following ACL injury is influenced by the initial treatment with Kenalog. Two years following ACL injury MRI analysis using standardized T2-mapping will be performed on 10 control subjects and 10 subjects who have received Kenalog injections.

INVESTIGATIONAL PLAN

Description of Overall Study Design and Plan (See Figure 1 for study timeline)

This study is a multicenter, randomized, placebo controlled, double blinded, clinical trial. This trial will enroll 68 subjects between the ages of 14 and 33. This trial will be conducted at two clinical centers, the University of Kentucky and Vanderbilt University, as well as established criteria and support of the Multicenter Orthopaedic Outcome Network (MOON). A sub-study involving extended follow-up of patients, 24 months post-surgery will occur at the University of Kentucky clinical center only. This sub-study will involve 20 subjects of the initial University of Kentucky cohort returning for one additional follow-up MRI.

Description of observations and measurements to be made in this study:

[figure not shown]

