All biomarker analyses in synovial fluid will be performed by co-Investigator [name] (Duke University).

A portion of previously collected samples will be de-identified and shipped on dry ice to Children's National Medical Center at George Washington University where they will undergo the SOMAscan™ assay. The latest version of the SOMAscan assay measures 1,129 protein analytes in only 150 µl of serum. The assay offers exceptional dynamic range, quantifying proteins that span over 8 logs in abundance (from femtomolar to micromolar), with low limits of detection (38 fMol media LOD) and excellent reproducibility (5.1% median %CV) (<http://www.somalologic.com/Technology/SOMAscan-basic-info.aspx>). Once the analyses are complete any remaining samples at National Medical Center will be destroyed. At no time will anyone at Children's National Medical Center have access to subject identifiers or any other subject data.

Randomization: Patients will be randomized into one of four groups, and there will be 17 subjects per group.

- Group 1: will receive injection of Triamcinolone (40 mg) at time point 1 (1-2 days post injury) and saline placebo at timepoint 2 (12-14 post injury).
- Group 2: will receive a saline placebo injection at time point 1 (1-2 days post injury) and 40 mg Triamcinolone at time point 2 (12-14 days post injury.)
- Group 3: will receive two consecutive injections of 40 mg Triamcinolone, the first at time point 1 and the second at time point 2.
- Group 4 (control group): will receive two consecutive injections of saline placebo. The first at time point 1 and the second at time point 2.

Duration of Patient Enrollment: All subjects enrolled in the study will be followed for six months. Those subjects enrolled at the University of Kentucky site will be followed for 24 months, and 20 subjects from the main study will be recruited and enrolled in the extended follow-up MRI sub-study.

Duration of Study: Study duration will be 36 months from the commencement date. This duration may be extended to reach desired enrollment.

Data Safety and Monitoring Board (DSMB) - A DSMB consisting of 5 individuals (will monitor the study semi-annually and review reportable adverse events to the FDA as well as Vanderbilt and University of Kentucky Institutional Review Boards (IRBs). One of these members will maintain the allocation strategy, available upon request from the DSMB.

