Reasons for study withdrawal may include the following:

- Adverse event
- Non-compliance with protocol/protocol deviation
- Sponsor's decision
- Lost to follow up
- Withdrawal of consent

Subjects who are withdrawn or terminate early from the study will be replaced under certain circumstances. These circumstances are withdrawal prior to the completion of all three blood and synovial fluid draws (the study is powered to show a difference in these markers and will be underpowered if these subjects cannot be replaced)

The date and reason must be recorded for all subjects who withdraw from the study. If the reason for withdrawal is a treatment-emergent AE, the specific AE will be identified on the CRF and every attempt will be made to follow the event until resolution.

In addition, every attempt should be made to complete the Visit 6/Early Termination assessments.

If a subject discontinues the study for any reason prior to Visit #5/12-14 weeks post injury visit, then the collected data will be included in the safety analysis, however will not be included in the overall efficacy analysis and a replacement subject will be enrolled in the study.

STUDY PROCEDURES/EXAMINATIONS (See Appendix A)

Demographics, medical history and medication history: Demographic data to be collected on screening visit will include height, weight, date of birth, age, gender and race. Detailed past medical history and medication history will be collected on screening visit. The medical history or concurrent medication history will be noted on each visit.

Knee Aspiration: All subjects undergo knee aspiration to dryness at initial encounter (1-4 days after ACL injury), (+/- 4 days), 12-14 days after injury, at the time of surgery. Should a subject be enrolled into the study and choose not to undergo ACL reconstruction, subject will received treatment according to this protocol but, aspiration at time of surgery will be omitted. Planned aspiration postoperatively will not be performed unless clinically necessary for significant postoperative effusions. If an aspiration is done, a sample will be retained for analysis.

Visit 1 Screening (1-4 days post injury) (+/- 4 days): Upon arriving at the study clinic potential subjects will have the following assessments: range of motion, knee instability

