(Lachman's test) and standardized Flexion weight bearing x-rays. At this time the subjects will also be asked to fill in a standard questionnaire covering the KOOS, IKDC, SF-36 and, the catastrophizing scale, CSQ and a Likert pain scale.

All subjects must have a clinical exam that is consistent with an ACL tear. Following the review of above assessment results, review of inclusion/exclusion and after signing the informed consent/assent the following assessments will take place:

Collection of urine and 10 cc of blood for laboratory testing, partial Medical history, concomitant medications, demographic, BMI, smoking status, outcomes, and pain questionnaires will also be collected.

Subjects will then be randomized into and one of four treatment groups and undergo a knee aspiration. Following randomizing, the subject will receive their first dose study medication.

Visit 2 (12-14 days post injury):

- Lab tests(urine and 10 cc of blood)
- Pain Questionnaires administered
- Knee aspiration
- Study medication injection
- Patient reported outcomes (PROs) administered

Visit 3 (day of surgery)

- Lab tests(urine and 10cc of blood)
- Pain Questionnaires administered prior to surgery
- Knee aspiration (in the operating room under anesthesia)
- Patient reported outcomes (PROs) administered prior to surgery

Visit 4 (1-2 weeks post surgery)

- Pain Questionnaires administered
- Knee aspiration (if clinically indicated)
- Patient reported outcomes (PROs) administered

Visit 5 (4-6 weeks post surgery)

- Patient reported outcomes (PROs) administered
- Pain Questionnaires administered

Visit 6 (6 months follow-up/Early Termination Visit)

- Patient reported outcomes (PROs) administered
- Pain Questionnaires administered

Visit 7 (24 (+/- 3) month follow-up – completed via mail)

- Patient reported outcomes (PROs) administered
- Pain Questionnaires administered

Visit 8 (24 (+/- 3) OPTIONAL EXTENDED FOLLOW-UP SUB-STUDY TO INCLUDE 20 SUBJECTS)

- Research Specific MRI

ADVERSE EVENTS

Any significant change in a subject's health from screening will be recorded and reported as adverse events while the subject is taking part in the study. Adverse Events (AEs) will include

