Appendix A: Study Flow Chart

	Study Drug Treatment		Surgery ^s	Follow-up				Extended Follow-up Sub-Study
	Screening Baseline 1-2 days post injury (+/- 4 days)	12-14 days post injury		1-2 Weeks post surgery	4-6 weeks post surgery	6 Months Follow-up/Early Termination Visit	24 Months (+/-3) post surgery	24 Months (+/-3) post surgery
Study Time points	Time point 1	Time point 2						
Procedures	Visit 1	Visit 2	Visit 3	Visit 4	Visit 5	Visit 6	Visit 7 (out of office)	Visit 8 (MRI)
Informed Consent	X							X
Partial Medical History	X						X	
Medication History	X	X	X	X	X	X	X	
Smoking Status	X							
BMI Measurement	X							
Demographics	X							

X-Ray ¹	X							
MRI ^{2,6}	X							X
Range of Motion	X							
Knee Aspiration	X	X	X ^{3&5}	X ^{3&5}				
Randomization	X							
Study Medication	X	X						
Laboratory Tests								
Urine	X	X	X					
Blood	X	X	X					
Questionnaires And Scales								
Likert Pain Scale ⁴	X	X	X	X	X		X	
CSQ	X	X	X	X	X		X	
KOOS	X	X	X	X	X		X	X
IKDC	X	X	X	X	X		X	X
SF 36	X	X	X	X	X		X	
Catastrophizing Scale	X	X	X	X	X		X	
MARX Activity Scale								X

1 – All subjects must have standardized Flexion weight bearing x-rays. *Documentation of closed growth plates at screening will be noted on the routine SOC x-rays.*

2 - All subjects enrolled will have an MRI performed as a routine diagnostic tool regardless if surgery is to be scheduled or not. However, randomization can be performed prior to MRI as

the MRI examination is not necessary or required to diagnose the ACL tear.

3 – Knee aspiration will only be performed if the subject has –post-op fluid on the knee. Should a subject be enrolled into the study and choose not to undergo ACL reconstruction aspiration at time of surgery will be omitted.

4 - All subjects enrolled into the study must have been diagnosed with an ACL tear.

5 - Should a subject be enrolled into the study and choose not to undergo ACL reconstruction, subject will received treatment according to this protocol

6- Subjects enrolled in the extended follow-up sub-study will undergo a research specific MRI, that is not considered standard of care.

References:

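### The text on Visit 1 allows the first injection up to day 8, later than Appendix A and the objectives allow, and no minimum gap before the second injection is set

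*Combined protocol and SAP*

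**What the plan says.** The window for the first visit is stated in several places.

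- Study Procedures, Knee Aspiration: the initial aspiration is at "1-4 days after ACL injury), (+/- 4 days".
- Study Procedures, visit schedule: "Visit 1 Screening (1-4 days post injury) (+/- 4 days". The first dose belongs to this visit: "Following randomizing, the subject will receive their first dose study medication".
- Appendix A, Study Flow Chart: "Screening Baseline 1-2 days post injury (+/- 4 days".
- Objective 1: drug is given "within 1 week of ACL injury or at 2 weeks after ACL injury", or at both times.
- Objective 2: synovial samples are taken at "1-7 days, 10-17 days after injury and at time of surgery".
- Randomization: the first injection is at "time point 1 (1-2 days post injury", with no allowance stated.

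Visit 2, with the second injection, is at 12-14 days after injury in Randomization, Knee Aspiration, the visit schedule and Appendix A. It is counted from injury, not from the first dose. Group 3 "will receive two consecutive injections of 40 mg Triamcinolone, the first at time point 1 and the second at time point 2".

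The Dose paragraph under Limitations, potential problems, and alternatives considers a second injection 10 days after the first unlikely to damage cartilage or other joint tissue. No section sets a minimum interval between injections.

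The combined file holds three copies of the protocol, and the conflict between the Visit 1 text and Appendix A is in all three.

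**The concern.** There are two linked problems.

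First, the dosing rule contradicts itself. A subject first injected on day 8 complies with the Study Procedures text, but is two days late under Appendix A and one day outside both objectives. Sites and monitors cannot tell whether that is a deviation.

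Second, because Visit 2 is counted from injury, every day of delay in the first dose shortens the gap to the second. In Group 3 both injections are active. The Dose paragraph itself says the drug may persist in the joint longer than in the circulation, and the Study Medication section expects slow absorption from the injection site. The gap therefore bears on the local risk that the 10-day statement addresses. Staff are given no interval to check before injecting again.

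**Working it through.** All figures are whole-day arithmetic on the stated windows.

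**Reproducing the plan's 10 days.** Nominal timing in Randomization is day 1-2 for the first dose and day 12-14 for the second. Shortest gap = earliest Visit 2 - latest Visit 1 = 12 - 2 = 10 days; longest = 14 - 1 = 13 days. So 10 days is the shortest gap on the nominal schedule.

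**Latest first dose.**
- Study Procedures text: 4 + 4 = day 8
- Appendix A: 2 + 4 = day 6
- Objectives 1 and 2: day 7

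The text exceeds Appendix A by 8 - 6 = 2 days and the objectives by 8 - 7 = 1 day.

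**Shortest permitted gap, with Visit 2 on day 12.**
- Study Procedures text: 12 - 8 = 4 days, which is 6 short of 10
- Objective 1 limit: 12 - 7 = 5 days
- Appendix A: 12 - 6 = 6 days, which is 4 short of 10

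**Gap by day of first dose, and earliest Visit 2 under a 10-day rule.** Earliest Visit 2 = max(12, first-dose day + 10).

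| First dose (day) | Gap, Visit 2 day 12 | Day 13 | Day 14 | Earliest Visit 2 with 10-day rule |
|---|---|---|---|---|
| 1 | 11 | 12 | 13 | 12 |
| 2 | 10 | 11 | 12 | 12 |
| 3 | 9 | 10 | 11 | 13 |
| 4 | 8 | 9 | 10 | 14 |
| 5 | 7 | 8 | 9 | 15 |
| 6 | 6 | 7 | 8 | 16 |
| 7 | 5 | 6 | 7 | 17 |
| 8 | 4 | 5 | 6 | 18 |

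From day 5 on, no Visit 2 date in the 12-14 day window gives 10 days. Days 5 and 6 are allowed by Appendix A, so adopting its window does not by itself secure the 10-day gap.

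**Fit with the sampling window.** Objective 2 places the second sample on days 10-17. With a 10-day rule, the latest Visit 2 is day 16 if the first dose is capped at day 6 and day 17 if capped at day 7; both fit. If day 8 were kept, Visit 2 would fall on day 18, one day outside.

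**The case against.** The strongest reply is that this is a corner case with no documented harm. Patient Population says that subjects are typically referred within 48 hours, so most first doses should be near day 2 and most gaps near 10 days or more. The Study Stopping Criteria also act between doses: local intolerance, any allergic sign, any serious adverse event after an injection, or symptoms that prevent the second one. Both points stand and limit the consequence. Neither supplies an interval, and neither resolves the contradiction in the Visit 1 window.

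It is also fair to say that the Dose paragraph is not wrong. It is right for the nominal schedule, sets no minimum, and is silent on the 4-day allowance. Nor is it the protocol's only remark on repeat dosing: the Pediatric dosing paragraph mentions two local administrations when it discounts an effect on growth. That remark concerns growth and names no interval, so the Dose paragraph remains the only statement on local cartilage harm.

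The other statements of the first-dose window are compatible rather than identical: day 2 with no allowance in Randomization, day 6 in Appendix A, day 7 in the objectives. A day-7 cap would satisfy the objectives as well as day 6 does.

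A reader might infer three stronger things that the documents do not support:

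- **That a 4- or 6-day gap endangers subjects.** Nothing in the documents shows this; 10 days is the protocol's own assumption.
- **That Group 3 will usually be dosed at such gaps.** The referral statement points the other way.
- **That the gap could fall to 2 days (10 - 8), from the day-10 lower limit in objective 2.** That limit is a sampling window; the dosing schedule says 12-14 days throughout.

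**Conclusion.** The point holds as an inconsistency in the dosing rule and a gap in the dosing schedule. The Study Procedures text permits a first dose two days later than Appendix A and one day later than the objectives. The shortest permitted interval between the two 40 mg doses in Group 3 is 4 days under the text and 6 under Appendix A. The 10 days behind the cartilage statement is not guaranteed under either.

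This rests on reading the allowance as added to the upper end of each stated range, and on Visit 2 staying at 12-14 days from injury. It affects late presenters in one arm of 17. The number of late presenters cannot be estimated from the documents but should be small. It should be corrected because the rule cannot be followed consistently as written and the correction is cheap.

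**What to change.** 1. In Knee Aspiration and in Visit 1 Screening, replace the window with Appendix A's, ending on day 6. A day-7 cap would also satisfy the objectives, provided it is stated both there and in Appendix A.
2. Require at least 10 days between the two injections in all four arms, so that the timing of Visit 2 does not hint at allocation. Let Visit 2 run past day 14 when needed, to day 16 at most (day 17 with a day-7 cap). Amend the Visit 2 timing in Randomization, Knee Aspiration, the visit schedule and Appendix A to match.

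The cost is wording, slightly more spread in Visit 2 dosing and sampling for subjects first dosed on day 5 or later, and the loss of the few first seen after the cap (days 7-8, or day 8 only with a day-7 cap). No new data are needed.

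The alternative is to leave Visit 2 at 12-14 days and restate the Dose paragraph for the 6-day minimum that Appendix A's window allows. That is more than an edit: it is acceptable only if the sponsor can justify the shorter gap clinically, and the protocol does not now do so.

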Sample Size and Power Analysis - We used the VAS and WOMAC data from Chevalier et al. as the template for power calculations [4] and the change in KOOS pain and ADL from our study. Chevalier reported a 53% response rate by VAS. Response was defined as a 50% improvement in VAS pain score from baseline. We observed comparable differences in our study (20-30% between outcomes in the IL-1Ra and placebo groups); therefore this dataset is reasonable to estimate study power. Based upon the change in VAS pain score in the Chevalier study, and conservatively estimating a placebo response rate of 30%, the effect size was 0.47 for a dichotomous outcome. At this effect size power for a sample size of 17/group is reasonable (65%) for the weakest possible outcome (i.e., one that only generates a "yes" or a "no" for each patient). Moreover, power is excellent for the continuous KOOS outcomes. With 17 patients per group we achieve 90% power for effect sizes of approximately 0.77 and 80% power for effect sizes of approximately 0.65. These latter effect sizes are in standard deviation multiples. So, for example, if the standard deviation of the VAS is approximately 20, and we expect an improvement of approximately 20 units in the intervention group, we can tolerate an improvement of approximately 7 units in the placebo group and still have 90% power (i.e. the effect size is $(20-7)/20 = 0.65$). Moreover, using the effect size standard benchmarks of 0.50 as moderate and 0.80 as large, we will be powered to detect moderate-to-large effects of the intervention, which is consistent with intuition for a study of this size. Power calculations based on our pilot KOOS data confirm this estimate. The change in KOOS (days 0-4) comparing treatment and placebo groups yielded an effect size of 0.62 for pain and 1.08 for ADL. At a

group size of 17 we will have 80% power to detect a difference in KOOS pain and >99% power to detect a difference in KOOS ADL.

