The power calculations include several caveats. The power calculation was performed based upon the use of a IL-1 receptor antagonist. There is no clinical data available in a young patient population with knee ligament injuries regarding their pain improvement after cortisone injection. The IL1RA data is the most comparable. Cortisone is a wider spectrum anti-inflammatory than IL-1RA and thus may have a larger effect on pain control that may be longer lasting. In that case our study may be over-powered. First, for purposes of power calculation, we have not assumed a full repeated measures analysis, but have instead analyzed change from baseline at a single time point. Second, we note that in trials such as this, the power of a non-parametric analysis is never much lower than its parametric analog (the "asymptotic relative efficiency" of the Wilcoxon test is at least 0.95), leading us to conclude that our parametrically based power calculations should apply with equal force to a non-parametric analysis.

Statistical analyses - Results from a sample of this size may not be normally distributed. Therefore, non-parametric statistical measures may be used. Primary outcome measures evaluating for change in KOOS and IKDC will be assessed at multiple points and will be analyzed for change between groups using Friedman two-way ANOVA for repeated measures. Synovial fluid analyses comparing the three groups at three time points will be analyzed using the Wilcoxon Signed Rank Sum Test with Hochberg corrections for multiple time points. Alternatively, if results are normally distributed or can be transformed (e.g., by log transformation) to meet the criteria for normality for parametric analysis, then repeated measures ANOVA will be utilized comparing treatment groups. P-values of less than or equal to 0.05 will be considered statistically significant. For those subjects enrolled in the extended follow-up sub-study the 24 month time point will be examined as an additional time point. Additionally, correlation analyses will be used to examine the relationship between biomarkers collected at Visits 1-3 and KOOS and IKDC values and MRI findings at 24 month follow-up.

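### None of the power figures stated for 17 per group is what a 17 v 17 comparison gives (KOOS pain about 42%, not 80%), and one effect size is assigned both 80% and 90% power

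*Combined protocol and SAP*

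**What the plan says.** The Randomization paragraph sets the design: "Patients will be randomized into one of four groups, and there will be 17 subjects per group". The Sample Size and Power Analysis section then makes five power statements for that group size:

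- Binary response, 53% v an assumed 30% on placebo, effect size 0.47: "At this effect size power for a sample size of 17/group is reasonable (65%) for the weakest possible outcome".
- Continuous outcomes in general: "With 17 patients per group we achieve 90% power for effect sizes of approximately 0.77 and 80% power for effect sizes of approximately 0.65". The next sentence says that these effect sizes are in SD units.
- Worked example with SD 20 and 20 units of improvement on active treatment: "we can tolerate an improvement of approximately 7 units in the placebo group and still have 90% power". The effect size is given as (20-7)/20 = 0.65.
- Pilot basis for KOOS pain: "The change in KOOS (days 0-4) comparing treatment and placebo groups yielded an effect size of 0.62". The corresponding ADL value is 1.08.
- KOOS power, the second figure being for ADL: "group size of 17 we will have 80% power to detect a difference in KOOS pain and >99% power to detect a difference".

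The caveats add that the calculation is parametric, on change from baseline at one time point, without a repeated-measures gain. They also say that a steroid may have a larger effect than the IL-1 receptor antagonist from which the effects are borrowed: "In that case our study may be over-powered". The Statistical analyses paragraph sets the threshold: "P-values of less than or equal to 0.05 will be considered statistically significant". It does not say whether tests are one- or two-sided. The same power text appears in each copy of the protocol in the combined document.

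**The concern.** The inputs describe a two-group comparison of 17 v 17, and 80% power at 0.62 SD is implausible at that size. The text also contradicts itself without any calculation: 0.65 SD has 80% power in one sentence and 90% power two sentences later.

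Change in KOOS is named among the primary outcomes, so these figures frame how its result will be read. A null KOOS pain result from a trial described as having 80% power, and possibly more than it needs, looks like evidence against benefit. If power at the pilot effect is nearer 40%, a null result is more likely than not even when that effect is real. The protocol also says that the study will inform a larger randomised trial. If that trial were sized by the same method, the error would carry over.

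A second problem concerns timing. The KOOS effect sizes are for change over days 0-4. In this trial KOOS is completed at Visit 1, before the first injection, and next at Visit 2, 12-14 days after injury.

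**Working it through.** **Inputs from the plan.** n = 17 per group; alpha 0.05; standardised differences d = 0.62, 0.65, 0.77 and 1.08; response rates 53% and 30%; SD 20 in the worked example. Two-sided testing is my assumption, and one-sided results are shown as the range. I assume 17 evaluable per group, the most favourable reading, since early discontinuations are replaced.

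**Continuous outcomes.** For two independent groups of n, the noncentrality is d × sqrt(n/2) = d × sqrt(8.5) = 2.915d, with 2n − 2 = 32 degrees of freedom. The critical t is 2.037 (two-sided) or 1.694 (one-sided). For KOOS pain, 2.915 × 0.62 = 1.81, which lies below the two-sided critical value, so power must be under one half.

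| Statement | d | Noncentrality | Stated | Two-sided | One-sided |
|---|---|---|---|---|---|
| KOOS pain | 0.62 | 1.81 | 80% | 41.8% | 54.9% |
| General | 0.65 | 1.90 | 80% | 45.2% | 58.3% |
| Worked example | 0.65 | 1.90 | 90% | 45.2% | 58.3% |
| General | 0.77 | 2.24 | 90% | 58.6% | 71.0% |
| KOOS ADL | 1.08 | 3.15 | >99% | 86.3% | 92.5% |

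**Binary outcome.** The plan's 0.47 reproduces as Cohen's h: 2·arcsin(√0.53) − 2·arcsin(√0.30) = 0.4716. Then z = 0.4716 × sqrt(8.5) = 1.37. Power is 28% two-sided or 39% one-sided; Fisher's exact test, two-sided, gives 18%. The stated figure is 65%.

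**What 17 v 17 can detect, two-sided.** 0.99 SD at 80% power and 1.15 SD at 90%. At the section's own benchmarks, power is 29% at 0.50 (moderate) and 62% at 0.80 (large).

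**Numbers needed for the stated powers, two-sided.** 42 per group for 80% at 0.62; 39 for 80% at 0.65; 37 for 90% at 0.77; 33 for 99% at 1.08; about 50 for 65% on the binary outcome.

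**The worked example.** By the section's own statement, 90% power needs 0.77 SD, that is 0.77 × 20 = 15.4 units. The tolerable placebo improvement would then be 20 − 15.4 = 4.6 units, not 7. On the correct calculation, 90% needs 1.147 × 20 = 22.9 units, more than the whole 20-unit improvement. With no placebo improvement at all (d = 1.0), power is 81%.

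**Where the stated figures may come from.** A one-sided, one-sample t test with n = 17, noncentrality d × sqrt(17), gives 79%, 82%, 92% and 99.5% at 0.62, 0.65, 0.77 and 1.08. That is close to the stated values and would mean that the factor 2 in the variance of a between-group difference was left out. The binary figure comes out at 62% this way, not 65%, so this is an inference only.

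**Other designs, for KOOS pain at 0.62.** Pooled active against placebo, 51 v 17: 59% two-sided, 71% one-sided. A 34 v 34 contrast: 71% two-sided, 81% one-sided.

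**The case against.** Several points on the other side are fair.

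- **Sidedness is not stated.** One-sided testing cuts the KOOS pain shortfall from 38 to 25 points. It still delivers none of the stated figures.
- **KOOS ADL survives in substance.** At 86% it stays above 80%. The stated figure is wrong, but that outcome is not poorly powered at the pilot effect.
- **A more efficient analysis could do better.** A one-sided 34 v 34 contrast reaches 81% at 0.62, and baseline adjustment with a correlation near 0.8 gives 83% at 17 v 17. The section specifies 17 per group and an unadjusted change at one time point, and it describes no pooled contrast, so neither supports its figures.
- **The effect sizes are borrowed.** The section admits this, and the pilot effects are for another time window. The 42% is therefore power at an assumed effect, not a known property of the trial.
- **The remark on excess power is conditional** on a larger steroid effect. At 1.5 SD, 17 v 17 would indeed have 99% power. But the remark starts from figures that are themselves too high.
- **No analysis or stopping rule uses these powers.** That limits the harm to interpretation and future planning. How the sponsor would read a null result, or size the next trial, is a risk rather than something the plan states.

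One consideration runs the other way. Three active arms are compared with one placebo arm. Bonferroni adjustment for three comparisons would lower KOOS pain to 25% and KOOS ADL to 73%, so the unadjusted figures are generous.

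**Conclusion.** The concern holds. No stated power is delivered by a 17 v 17 comparison under either sidedness. Two-sided, the shortfall is 38 points for KOOS pain, 35 at 0.65, 31 at 0.77, 45 in the worked example, 37 for the binary outcome and about 13 for KOOS ADL. The double assignment of 0.65 to 80% and 90% is an error on the face of the text.

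The recomputed values rest on the plan's own effect sizes, an unadjusted t test at 0.05 and 17 evaluable per group. The conclusion does not depend on how the error arose. The KOOS figures also rest on a days 0-4 effect that the visit schedule does not measure, so even the corrected values are conditional on that effect persisting to Visit 2. This must be corrected because it changes what a null KOOS pain result can support.

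**What to change.** Keep the sample size and rewrite the section:

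1. State the test, the sidedness and the absence of multiplicity adjustment. For 17 v 17 at two-sided 0.05, give 42% for KOOS pain (0.62), 86% for KOOS ADL (1.08), 45% at 0.65, 59% at 0.77, and about 28% for 53% v 30% responders (18% by Fisher's exact test). Give detectable differences of 0.99 SD (80%) and 1.15 SD (90%). One-sided values may be added if one-sided testing is intended.
2. Correct the 20 v 7 example to 45%.
3. Remove the statements that KOOS power is excellent and that the trial can detect moderate-to-large effects. Remove the remark on excess power, or tie it to a named effect size with its recomputed power.
4. Say that the pilot effects are for days 0-4 and that the first post-injection KOOS here is Visit 2.
5. If the plan adopts a Visit 2 contrast of all who received triamcinolone at the first injection against all who received saline (34 v 34, KOOS completed before the second injection), quote 71% for 0.62 and 99% for 1.08, two-sided.

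The cost is one reworded section with less favourable figures. No patients, visits or procedures change.
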